3.0 Objectives

We will compare outcomes among Veterans with or at risk for CVD at three VA sites randomized (at the site-level) to one of three arms: 1) unmet needs screening only, 2) screening + provision of tailored resource sheets to address identified unmet needs, or 3) screening + tailored resource sheet + social worker support. We will quantitatively examine associations of unmet needs with baseline and follow up outcomes, assessing the impact of varying intensity referral approaches. We will also qualitatively examine stakeholder perspectives about the barriers and facilitators to identifying and addressing unmet needs to provide insight into the relative success of each study arm. Specific aims are:

Aim 1: Describe the prevalence and distribution of nine unmet needs (housing, food insecurity, utility insecurity, transportation, legal needs, employment, safety, social isolation, stress), and identify their associations with baseline sociodemographic characteristics, adherence, utilization and clinical outcomes.

Aim 2: Compare the effectiveness of varying intensity referral strategies to address unmet needs on the primary outcome of connection to new resources to address unmet needs, and on secondary outcomes of post-intervention change in unmet needs, adherence, utilization, and clinical outcomes. **H1.** Based on Maslow's model, we hypothesize that referrals (and more so for those enhanced by SW support) will increase the likelihood of patients connecting to new resources to address unmet needs (primary outcome), which may then have positive sequential effects, with reduced unmet needs, increased adherence, decreased urgent care/preventable utilization, and ultimately, improved clinical outcomes.

Aim 3: Identify barriers and facilitators to Veterans' connecting with resources to address unmet needs and getting needs met, and explore potential explanatory factors related to the relative success of each study arm.

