5.0 Study Procedures

5.1 Study Design

To assess the efficacy of systematic S&R, we propose a two-phase, three-year mixed methods study (Phase One: quantitative, Phase Two: qualitative) to systematically screen Veterans with or at risk for CVD for nine unmet needs, characterize the prevalence of unmet needs and association with outcomes, and compare the effects of two different referral interventions of varying intensity on multiple outcomes.

In **Phase One (Aim 1)** we will survey Veterans about their unmet needs (N=1760) and conduct quantitative analyses of survey, administrative, and clinical data to characterize the prevalence of unmet needs and their association with baseline outcomes (adherence, utilization, and clinical). In **Phase One (Aim 2)**, we will implement a three-armed RCT at three VA sites to compare outcomes among Veterans with one or more unmet needs (N=880) randomized within each site to one of three intervention arms. Trial participants will participate in three surveys, all administered by phone: 1) an initial index unmet need survey; 2) an eight week follow-up survey to assess if participants connected to any new resources since the index screen and if so, to which one(s); and 3) six months after the initial index screen, the unmet need survey will be administered again.

We have the following study arms: 1) Unmet needs screening and provision of a post card with a generic list of VA resources (hereafter: "Screening" arm), 2)

Screening and provision of a post card with a generic list of VA resources plus provision of a tailored Resource Sheet listing available resources to address identified unmet needs (hereafter: “Awareness” arm), or 3) Screening and provision of generic list of VA resources plus provision of a tailored Resource Sheet plus research team SW-supported referral to assist with connection to resources for unmet needs (hereafter: “Assistance” arm). Quantitative analyses will longitudinally compare the effects of the two referral approaches of varying intensity and a generic intervention on the primary outcome of connections to new resources and secondary outcomes of reduction in unmet needs, adherence, utilization, and health outcomes. See **Appendix A** for a more detailed description of the intervention and approach to randomization.

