5.6 Data Analysis

Study Sample and Power Analysis

We aim for a total of 880 Veterans enrolled in the RCT (293/arm) based on power analyses provided below. Based on the study team's prior primary care-based studies with a similar recruitment approach, we anticipate 80% of patients approached to complete the index screen will participate. Based on pilot data from the Bedford MA VA where 78% of Veterans reported one or more needs, we then conservatively estimate that 50% of Veterans screened will report at least one of the nine unmet needs for which we will screen.

Thus, to yield a final sample of 880 Veterans with at least one unmet need enrolled in the study, we anticipate needing to approach 2200 eligible Veterans (733/site, or ~3 patients/day/site) i.e., of 2200, 80% (1760) will agree to participate in the study and of these, 50% (880) will have one or more unmet needs and be eligible for the RCT. If the participation rate or proportion of Veterans reporting at least one unmet need is lower than expected, we will increase the number of Veterans that we approach. We reviewed VA administrative data to determine the anticipated weekly count of Veterans eligible per site to participate in the study and there are more

than enough eligible Veterans to approach for additional screening if needed. We also anticipate drop-out rates at the 8-week follow-up survey to assess connection to resources and the 6-month unmet needs re-screen, respectively. Though the study team's prior study achieved a 65% follow up participation rate, here we conservatively anticipate a 50% participation rate for both the 8-week follow-up survey and the 6-month re-screen, reducing the sample for the three arms first to 440 Veterans total and then to 220 Veterans total.

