Statistical Power for Aim 1: With a sample of N=1760 Veterans completing the index unmet needs screening, we will have 80% power to detect small effect sizes ($f^2=.01$; $OR=1.47$) using 2-tailed significance tests at the $\alpha=.001$ level if the intraclass correlation coefficient (ICC) (for the nesting of patients within sites) is negligible, or medium effect sizes ($f^2=.15$; $OR=4.07$) even if the ICC is as high as .02 for testing associations between the presence of each unmet need and sociodemographic, adherence, utilization, and clinical (BP only) variables. HbA1c is anticipated to be a relevant clinical outcome for only 40% of the sample; for HbA1c, we will have 80% power to detect small effect sizes ($f^2=.03$; $OR=1.84$) using 2-tailed significance tests at the $\alpha=.001$ level if the ICC is negligible.

Statistical Power for Aim 2: The power analysis for Aim 2 focused on the primary outcome of connection to resources to address unmet needs. The sample size was determined based on previous research outside VA which found that individuals who completed a screening and referral intervention were 15% more likely (adjusted Odds Ratio (aOR)=2.1) to have enrolled in a new community resource to address unmet needs post-referral compared to patients in the non-intervention arm. In the present study, we will have 80% power to detect an effect of this size (aOR=2.1) across the three arms using 2-tailed significance tests at the $\alpha=.05$ level, even if we assume an attrition rate as high as 50% for the follow-up phone call at 8-weeks post-screen (retained N=440 across all sites and arms) and a conservative ICC value for patients nested within sites of .01. Previous empirical work found ICC values <.0001 when adjusting for a small number of covariates (e.g., race, marital status) to examine new connections to resources to address unmet needs; we intend to collect and use these covariates in the present study as well. Assuming an ICC value of .0001, we will have 80% power to detect an effect as small as an aOR=1.7 if we assume a 50% attrition rate for the 8-week follow-up phone call, or as small as an aOR=2.0 if we assume a 70% attrition rate. We based our attrition rate upon the study team's prior study where Veterans

had low incomes, high unemployment and low educational status, yet only 35% were lost to a follow-up interview.

Quantitative Data Analysis

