Our primary Aim 2 analysis will compare *connection to new resources* at 8-weeks post-index screen (our primary outcome of interest) across the study arms. HGLM will be used to control for the nesting of patients within sites. In all models, patient-level intercepts and slopes will be treated as random effects. We predict significantly greater connection to new resources in the ASSISTANCE arm

compared to the SCREENING arm, with the AWARENESS arm falling intermediate to these other two study arms.

Adherence, Utilization, and Clinical Outcomes. We will also conduct a series of secondary analyses to examine whether the study arms influence more distal outcomes, including adherence, utilization, and clinical outcomes. Specifically, to assess the impact of our intervention on more distal healthcare outcomes, we will use a difference-in-difference approach to examine whether changes from baseline at 6-months and 12-months post-referral differ across the three arms of our RCT (N=880). A series of HLM/HGLM analyses with patients nested within sites will examine differences in change from baseline across arms for the adherence, utilization, and clinical outcomes. As with the other analyses, all models will treat patient-level intercepts and predictors as random effects. We will have 80% power to detect small-to-medium effects ($f^2=.05$; OR=2.28) across the three arms using 2-tailed significance tests at the $\alpha=.05$ level, even if we assume a conservative ICC value for patients nested within sites of .01. HbA1c is anticipated to be a relevant clinical outcome for only 40% of the sample and we anticipate missing HbA1c test data for 17% of these Veterans in the year following their index screen; thus, for HbA1c, we will have 80% power to detect small-to-medium effects ($f^2=.08$; OR=2.71) across the three arms using 2-tailed significance tests at the $\alpha=.05$ level, even if we assume a conservative ICC value for patients nested within sites of .01.

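### The 80% power claimed for aOR 1.7 (440 retained) and aOR 2.0 (264 retained) is not reached by any comparison of three equal arms: at most about 63% for Assistance v Screening, about 75% for both referral arms pooled

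*Combined protocol and SAP*

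**What the plan says.** Section 5.6 sets the enrolment: "We aim for a total of 880 Veterans enrolled in the RCT (293/arm"). It expects half to answer the 8-week survey, which leaves 440. The effect that sets the sample size comes from earlier research outside VA, given as an odds ratio of 2.1 against a non-intervention arm. For it the plan states that "we will have 80% power to detect an effect of this size (aOR=2.1) across the three arms", two-tailed at .05, with 440 retained and an ICC of .01.

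It then takes an ICC of .0001 and claims more: "we will have 80% power to detect an effect as small as an aOR=1.7 if we assume a 50% attrition rate", "or as small as an aOR=2.0 if we assume a 70% attrition rate". These two claims are the subject here.

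The primary Aim 2 analysis compares connection to new resources at 8 weeks, a yes/no answer in Appendix J. "We predict significantly greater connection to new resources in the ASSISTANCE arm" than in the Screening arm, with Awareness in between. For the distal outcomes, with all 880, the plan says: "We will have 80% power to detect small-to-medium effects ($f^2=.05$; OR=2.28) across the three arms", again at ICC .01.

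Section 5.6 gives no Screening-arm connection rate, contrast, degrees of freedom or power formula. On the unit of randomization, 3.0 has "at three VA sites randomized (at the site-level) to one of three arms" and 5.1 has "randomized within each site to one of three intervention arms".

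**The concern.** An odds ratio of 1.7 is a modest effect for about 147 per arm on a binary outcome, and 2.0 is modest for 88 per arm. Both figures looked too favourable for three arms, and more like what the same totals would give if split into two groups.

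These figures tell the DSMB and later readers how small an effect the primary analysis can detect and how much loss to follow-up it can absorb. If they are wrong, a null result could be read as evidence against an odds ratio of 1.7 when the trial had little better than an even chance of detecting it. A retention shortfall could also be accepted because the plan says that 70% attrition is tolerable.

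**Working it through.** **Inputs.** From 5.6: 880 enrolled in three equal arms; alpha .05 two-tailed (stated for aOR 2.1 and taken to carry over); ICC .0001; odds ratio against the non-intervention arm. Retained at 50% attrition: 440, or 440/3 ≈ 147 per arm. At 70% attrition: 880 × 0.30 = 264, or 88 per arm (derived; the plan does not print 264). The control rate is not stated, so it is scanned from 1% to 99%; 20-60% is used as an assumed working range.

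**Reproducing the plan's figures.** The plan pairs f² = .15 with OR 4.07, which fits OR = exp(2f·π/√3), that is, d = 2f followed by the logistic conversion. With three sites, take Neff = N/(1 + (N/3 − 1)·ICC) and a 2-df F test at 80% power:

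- N = 440: Neff = 440/1.0146 = 433.7; f² = .0224; OR = exp(2 × √.0224 × 1.814) = 1.72.
- N = 264: Neff = 264/1.0087 = 261.7; f² = .0372; OR = 2.01.

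These match 1.7 and 2.0. That this was the route is an inference, since the plan states none. The step d = 2f holds for two equal groups. With three equal arms whose largest difference is d, f is at most d·√2/3 = 0.471d (two arms equal), and d/√6 = 0.408d with the middle arm halfway. Splitting the whole sample into two groups gives the same impression: 220 v 220 at OR 1.7 has at most 79.2%, and 132 v 132 at OR 2.0 at most 80.0%.

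**Power with three arms.** Two-proportion normal approximation, no ICC inflation:

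power = Φ[(|p₂ − p₁| − 1.96·√(2p̄(1 − p̄)/n)) / √((p₁(1 − p₁) + p₂(1 − p₂))/n)]

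Example: OR 1.7, n = 147, p₁ = .40. Then p₂ = .53125 and p̄ = .4656; the standard errors are .0582 (null) and .0577 (alternative). (.13125 − 1.96 × .0582)/.0577 = 0.298, so power is 61.7%.

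| Assistance v Screening, control rate | OR 1.7, 147/arm | OR 2.0, 88/arm |
|---|---|---|
| 20% | 49.5% | 51.6% |
| 21.5% | 51.3% | 53.3% |
| 40% | 61.7% | 62.6% |
| 60% | 57.2% | 56.6% |
| Maximum over all rates | 62.0% | 62.6% |

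(21.5% is one control rate at which OR 2.1 equals +15 points: .215 to .365.)

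| Other comparisons | OR 1.7, N=440 | OR 2.0, N=264 |
|---|---|---|
| 2-df test, Awareness midway on the log-odds scale, control 20-60% | 40-51% | 42-52% |
| 2-df test, best case (Awareness equal to another arm) | at most 64% | at most 65% |
| Both referral arms pooled v Screening | at most 74.5% | at most 75.3% |

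**A bound free of the control rate.** Setting p(1 − p) to its maximum of .25 in every arm, pairwise power is Φ(ln OR·√(.25n/2) − 1.96), or 62% and 63%. The pooled 2:1 comparison, the most favourable single contrast, is Φ(ln OR·√(.25n·2/3) − 1.96), or 75% and 76%. No control rate rescues the claims.

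**Sample needed.** Pairwise 80% needs at least 225 per arm for OR 1.7 (147 available) and at least 133 per arm for OR 2.0 (88 available). At a control rate of 21.5% it needs 291 and 165.

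**The design effect, aOR 2.1.** At 147 per arm without ICC inflation, power is 80-89% pairwise and 71-82% for a 2-df test with Awareness midway (control 20-60%). With ICC .01 on the f² route it is 78% (1 df) or 68% (2 df). At 88 per arm, pairwise power is 58-68%.

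**Consistency across Aim 2.** At ICC .01 the plan gives OR 2.1 for 440 and the larger 2.28 for 880. With Neff 179 and 224, the f² route gives the reverse order at any fixed df: 2.15 v 1.98 (1 df), 2.34 v 2.13 (2 df), 2.47 v 2.24 (3 df).

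**The case against.** The strongest defence is that the plan works on the f² scale, speaks of power across the three arms, and never says that 1.7 is the largest odds ratio between two arms. On that scale a three-group F test does have about 78-80% power. This explains the figure but does not save it: the reader is given an odds ratio, and the preceding sentences define it against the non-intervention arm. An odds ratio per adjacent step (2.89 between extreme arms for 1.7) would give about 98%, but the text does not support that reading. One-sided testing of pooled arms would give up to 83-84%, but the plan says two-tailed. Covariate adjustment cannot exceed the bound above.

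Second, the inconsistency argument can be pressed too far. The 2.28 concerns different outcomes, and 2.1 is an effect from earlier research, not a computed minimum. At 3 df the f² route returns 2.71 for HbA1c (880 × .40 × .83 ≈ 292), 2.94 for 220, and 2.24 against the stated 2.28. So 2.71 and 2.94 follow their own route. That stands, and 2.28 beside 2.1 is not a strict impossibility. But those figures use the same two-group conversion, and the 2-df route behind 1.7 and 2.0 would give 2.34, not 2.1, at N = 440 with ICC .01.

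Third, aOR 2.1 should not be let off lightly. Its support depends on the control rate (58.5% pairwise at a rate of 10%) and on dropping the ICC of .01 that the plan attaches to it. If the 15% quoted with it is relative, the implied control rate is 75.1% and pairwise power is 69%. This stands and is reflected in the fix.

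Fourth, the site-level phrase in 3.0 is probably a slip, since 5.1, 5.2 and Appendix A all describe individual randomization. It does not affect 1.7 or 2.0 at ICC .0001, but it does bear on how the ICC of .01 should enter.

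**Conclusion.** The concern holds. With three equal arms, a binary outcome and two-sided alpha .05, the claims of 80% power for aOR 1.7 at 50% attrition and aOR 2.0 at 70% attrition are wrong as written. Actual power is at most 62-63% for the predicted contrast and at most about 75% for the most favourable one. These maxima need no assumption about the control rate. They assume only that the odds ratio is the largest between arms and that clustering costs nothing, which favours the plan. That the error lies in the f²-to-odds-ratio conversion is an inference, and the shortfall does not depend on it.

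The sample size is not overturned, because it rests on aOR 2.1. What disappears is the margin. At 70% attrition, Assistance v Screening has about 52-63% power for OR 2.0 and 58-68% for OR 2.1 (control rates 20-60%). Even at the prior study's 65% retention (880 × .65/3 ≈ 191 per arm), OR 1.7 has at most 73% for that contrast.

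**What to change.** In 5.6:

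- Name the primary contrast (for example Assistance v Screening, as predicted), its degrees of freedom and the assumed Screening-arm connection rate. Say whether the 15% from the earlier research is in percentage points or relative.
- State an ICC treatment that fits randomization within sites. If arm effects may vary by site (5.6 has random slopes; Appendix A has one social worker per site), state that variance.
- Recompute every Aim 2 figure by that one method. For Assistance v Screening without ICC inflation, at assumed control rates of 20-60%, replace 1.7 by about 1.9-2.1 (1.93-2.11, N = 440) and 2.0 by about 2.3-2.6 (2.34-2.57, N = 264). If the pooled contrast is chosen instead, the figures at the most favourable control rate and ICC .0001 are about 1.77 and 2.09.
- Keep 2.1 as the design effect, but restate its power under the chosen ICC treatment.
- Recompute 2.28, 2.71 and 2.94 by the same stated method for their own outcomes.

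In 3.0, bring the site-level phrase into line with 5.1.

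The cost is numbers and wording in 5.6 and one phrase in 3.0. No patients are added and the analysis does not change. The price is a less favourable statement of what the trial can detect.

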VAs' lack of systematic and comprehensive S&R for unmet needs also means missed opportunities to better understand the scope and scale of unmet needs across the entire VA patient population, as no such data exists.¹⁴ This in turn limits VA's understanding of how best to support and target SW services. It is also unknown whether a lower-intensity referral process (i.e., provision of tailored paper Resource Sheets to address unmet needs instead of a referral to SW) can help some Veterans to the same extent it helps patients in non-VA care settings.

^{10, 16} Thus, a critically important dimension of the study we propose is to test whether for some Veterans, a less intense intervention is adequate. If so, this has valuable implications for resource allocation decisions and future implementation.

To address these knowledge gaps, we propose a **randomized controlled trial (RCT)** to systematically screen Veterans with/at risk for CVD for nine unmet needs, characterize the prevalence of unmet needs and associations with outcomes, and compare the effect of two different intensity referral interventions. Our primary outcome is Veterans' connections to new resources to address unmet needs. Additional outcomes include unmet need reduction, adherence (medications, ambulatory care appointments), utilization (preventable hospitalizations, urgent care), and clinical outcomes (blood pressure, glycemic control).

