All data analysis will be conducted by study team members based in Boston. [name] is the study Data Analyst who will be responsible for developing the analytic data sets and all programming related to descriptive statistics and multivariate models. He will work closely with [name], the statistician who will be responsible for developing the statistical models and overseeing the overall analytic approach. All analysis will be conducted on VINCI.

Aim 1: Describe the prevalence and distribution of nine unmet needs (housing, food insecurity, utility insecurity, transportation, legal needs, employment, safety, social isolation, stress), and identify their associations with baseline sociodemographic characteristics, adherence, utilization and clinical outcomes.

Our primary analysis for Aim 1 will be descriptive. We will use data obtained during the index screening (N=1760) to generate descriptive statistics (e.g., proportions, 95% confidence intervals (CIs) to characterize the prevalence and distribution of each of the nine unmet needs at baseline across all study sites. We will next conduct inferential analyses to examine associations between unmet needs and sociodemographic characteristics as well as baseline outcomes (i.e., adherence, utilization, and clinical outcomes drawn from CDW data in the 12-months before the index screening for each Veteran). Hierarchical Linear Modeling will be used to control for the nesting of patients within sites, and patient-level variables will be treated as random effects. Hierarchical Generalized Linear Modeling (HGLM) will be used as appropriate to handle binary variables. Variables found to have statistically significant associations with unmet needs will be entered into multivariable models to better understand the correlates of each need. Bonferroni-corrected significance levels will control for multiple comparisons.

Aim 2: Compare the effectiveness of varying intensity referral strategies to address unmet needs on the primary outcome of connection to new resources to address unmet needs, and on secondary outcomes of post-intervention change in unmet needs, adherence, utilization, and clinical outcomes

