Appendix I: Index Unmet Needs Screening Tool

DEMOGRAPHICS

1. Please indicate which of following types of people currently live with you in your household (*check all that apply*)

- My spouse or partner
- My child(ren) under age 18
- My adult child(ren) age 18 or older
- My parent(s)
- Extended family
- Roommate(s) not related to me
- Other individuals

2. Overall, which one of the following best describes how well you are managing financially these days?

- Living comfortably
- Doing OK
- Just getting by
- Finding it difficult to get by

3. Are you of Hispanic or Latino origin or descent?

- Yes, Hispanic or Latino
- No, not Hispanic or Latino

4. What is your race? Please select all that apply.

- White
- Black or African-American
- Asian
- Native Hawaiian or other Pacific Islander
- American Indian or Alaska Native
- Other

5. What is your gender

- Man
- Woman
- Transgender man
- Transgender woman
- Non-binary
- Other

HOUSING AND UTILITIES

6. In the past 6 months, have you been living in stable housing that you own, rent, or stay in as part of a household?

- Yes
- No

7. Are you worried or concerned that in the next 2 months you may NOT have stable housing that you own, rent, or stay in as part of a household?

- Yes
- No

7a. (If Yes to Q6 or Q7): Are you already receiving assistance with your housing needs?

7b. (If Yes to 7a): Would you like additional assistance?

7c. (If No to 7a): Would you like assistance with your housing needs?

8. In the past 6 months has the electric, gas, oil or water company threatened to shut off service in your home?

- Yes
- No
- Already shut off
- Not applicable

8a. (If Yes/Already shut off): Are you already receiving assistance with your gas, oil or water company needs?

8b. (If Yes to 8a): Would you like additional assistance?

8c. (If No to 8a): Would you like assistance with your gas, oil or water company needs?

EMPLOYMENT AND FOOD

9. Are you currently:

- Employed for wages
- Self-employed
- Out of work for 1 year or more
- Out of work for less than 1 year
- A Homemaker
- A Student
- Retired
- Unable to work

9a. Do you want help finding or keeping work or a job (check all that apply)?

- Yes, help finding a job
- Yes, help keeping work
- I do not want or need help
- I am already receiving assistance with my employment needs

10. How often were the following statements true for you in the past 6 months?

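### Aim 1 uses single-step Bonferroni where Holm's procedure holds the same error rate and never rejects less, and the stated alpha of .001 is not tied to a named family of tests

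*Combined protocol and SAP*

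**What the plan says.** Section 5.6, Quantitative Data Analysis, Aim 1, makes the primary analysis descriptive. Inferential tests follow, relating each unmet need to two sets of variables: sociodemographic characteristics and baseline outcomes. Variables that reach significance are carried into multivariable models. The next sentence is the whole multiplicity plan: "Bonferroni-corrected significance levels will control for multiple comparisons". It gives no family, no number of tests and no stage of the analysis.

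Statistical Power for Aim 1, in the same section, reads "With a sample of N=1760 Veterans completing the index unmet needs screening", "we will have 80% power to detect small effect sizes ($f^2=.01$; $OR=1.47", and does so "using 2-tailed significance tests at the $\alpha=.001$ level if the intraclass correlation coefficient (ICC" is negligible. This is "for testing associations between the presence of each unmet need and sociodemographic, adherence, utilization, and clinical (BP only) variables". HbA1c has its own figure at the same alpha: OR 1.84 in 40% of the sample.

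The outcomes are listed in section 2.0 as "adherence (medications, ambulatory care appointments), utilization (preventable hospitalizations, urgent care), and clinical outcomes (blood pressure, glycemic control". Section 5.6 has no analysis list of sociodemographic variables. The nearest thing is the demographics block of Appendix I, which has five items: household, finances ("Overall, which one of the following best describes how well you are managing financially these days"), ethnicity, race and gender.

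**The concern.** There are two linked matters.

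First, the method. Single-step Bonferroni tests every hypothesis at .05/m. Holm starts at the same threshold and relaxes it after each rejection. Power is therefore given up with no gain in error control. This has a practical consequence because significance decides which variables enter the multivariable models, so a missed correlate drops out of the later analysis as well.

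Second, traceability. A Bonferroni level means something only once the family is named. Alpha .001 appears in the power statement, but nothing connects it to the tests that the plan lists. A reader cannot tell whether 80% is the power of the planned procedure, and an analyst would have to choose the family later.

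**Working it through.** **Inputs.** N=1760; HbA1c subset .40 × 1760 = 704; two-sided alpha .001; ORs 1.47 and 1.84 (section 5.6). Nine needs (section 5.6); six outcomes, two each for adherence, utilization and clinical (section 2.0); five demographic items (Appendix I). I count each demographic item as one variable.

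**Step 1: reproduce the plan's figures.** Convert with f² = (√3 · ln OR / 2π)². OR 1.47 gives f² = .01128 and OR 1.84 gives f² = .02825. Use a noncentral F test with λ = f²·N, so λ = .01128 × 1760 = 19.85 and .02825 × 704 = 19.89. With 2 numerator df (my inference; the plan does not state it), power at alpha .001 is 80.3% and 80.1%. For ICC .02 the design effect is 1 + (1760/3 − 1) × .02 = 12.71, the effective N is 1760/12.71 = 138, and f² = .15 gives 80.2%. All three stated Aim 1 figures reproduce. With 1 df and f² = .01 exactly, the first is 81.6%.

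**Step 2: count the tests.** Sociodemographic: 9 × 5 = 45. Outcomes: 9 × 6 = 54. Together: 9 × 11 = 99. Per need: 11.

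**Step 3: power by family, same formula, negligible ICC.**

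| Family | Tests | Alpha = .05/m | Power at OR 1.47, N=1760 |
|---|---|---|---|
| One per need | 11 | .0045 | 90.3% |
| Sociodemographic set | 45 | .0011 | 81.1% |
| Outcome set | 54 | .00093 | 79.8% |
| All tests pooled | 99 | .000505 | 74.9% |

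For HbA1c (OR 1.84, N=704), the outcome family of 54 gives 79.5% and the pooled family of 99 gives 74.6%. In the pooled case, 80% power needs OR 1.49 instead of 1.47, and 1.89 instead of 1.84 for HbA1c.

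**Step 4: Holm against Bonferroni.** Order the p-values and compare the i-th smallest with .05/(m − i + 1), stopping at the first failure. Every threshold is at least .05/m, so everything that Bonferroni rejects is rejected. When the first true null is rejected, all m₀ true nulls are still in play. The threshold is then at most .05/m₀, and the union bound gives a family-wise error of at most .05 under any dependence.

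The size of the gain comes from simulation: 20,000 runs, independent 2-df chi-square tests, and every true effect at λ = 19.85. Entries are average power per true association.

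| Share real | 99 tests: Bonferroni → Holm | 54 tests: Bonferroni → Holm |
|---|---|---|
| about 10% | 75.1% → 75.7% | 80.0% → 80.4% |
| 30% | 75.2% → 77.3% | 80.1% → 81.9% |
| 50% | 75.2% → 79.2% | 80.0% → 83.9% |
| 70% | 75.2% → 81.6% | 80.0% → 86.3% |

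With correlation .3 between tests, the gains are up to about 0.7 point smaller. Family-wise error stayed below 5% throughout. In a family of 11, the gain runs from almost nothing with one real association to about 2 points with five.

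**The case against.** The strongest defence is that nothing in the plan is invalid. Bonferroni controls the error it claims to control, it has simple matching simultaneous confidence intervals that Holm lacks, and choosing it is a preference. The tests follow a descriptive primary analysis, recruitment is driven by the 880 needed for the trial, and the Aim 2 primary outcome is not touched. The plan's own ICC caveat moves the detectable OR from 1.47 to 4.07, far more than any choice of family does. All of this stands and limits the weight of the point. It does not answer the fact that, for testing, Holm rejects at least as much at the same error rate.

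A reader might infer more: that .001 is Bonferroni for 50 tests (.05/.001 = 50), that the plan lists 99, and that the true power is therefore 75%. The documents do not support this. The figure of 50 appears nowhere and is only back-calculated. The plan never pools all need-by-variable tests. It names two sets, and with a family for each, power is 81.1% and 79.8%, so the stated 80% holds with every counted variable included. With one family per need, .001 is stricter than required. Nor is 99 a settled count. Appendix I is a questionnaire, not an analysis list, and marital status, named as a covariate in the Aim 2 power paragraph, would make it 9 × 12 = 108.

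A reader might also infer that Holm would restore whatever a pooled family costs. In general it would not. Over 99 tests the threshold returns to .001 only after 49 rejections (.05/(99 − 49)), and with few real associations the gain is under one point.

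**Conclusion.** The point holds as a modest improvement to a stated method plus a needed clarification. Holm is the better testing procedure whichever family is meant. In a family of 99 or 54 it is worth under 1 point of average power if about 10% of associations are real, and about 2, 4 and 6 points at 30%, 50% and 70%. The stated 80% is not shown to be wrong. It cannot be traced to a family, and the admissible readings run from about 75% to about 90%.

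These sizes assume negligible ICC, 2-df tests, each demographic item as one variable, and all true effects at OR 1.47 with the full N=1760. The last is a simplification for HbA1c, which has 704. The share of real associations is unknown, so the gain is given as a range.

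**What to change.** In section 5.6, Aim 1 analysis, replace the Bonferroni sentence with one that applies Holm's step-down procedure at family-wise .05, names the family (which needs, which variables, how many tests) and says that it governs the tests that select variables for the multivariable models. Add that intervals will be reported either unadjusted or at the Bonferroni level, since Holm has no simple matching simultaneous set.

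In Statistical Power for Aim 1, state alpha as .05 divided by the size of that family and give the matching power at OR 1.47:

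- separate sociodemographic and outcome families: about 80%;
- one family per need: about 90%;
- a single family of 99: about 75%, with 80% at OR 1.49 (HbA1c 1.89). Use this only if one pooled family is intended.

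List the sociodemographic variables so that the count is fixed before analysis. The cost is a few sentences, with no new data and no change to the sample size. The loss of matching simultaneous intervals is the only drawback.
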